### THROMBOCYTOPENIA

Preferred term	PT code
bleeding time abnormal	10049227
bleeding time prolonged	10005140
coagulation test abnormal	10063557
platelet count abnormal	10035526
platelet count decreased	10035528
platelet disorder	10035532
platelet dysfunction	10073391
thrombocytopenia	10043554
thrombocytopenic purpura	10043561

### LOWER RESPIRATORY TRACT INFECTION

Preferred term	PT code
atypical pneumonia	10003757
bronchitis	10006451
bronchitis viral	10053160
haemorrhagic pneumonia	10077933
lower respiratory tract infection	10024968
lower respiratory tract infection viral	10065188
lung infection	10061229
pneumonia	10035664
pneumonia respiratory syncytial viral	10035732
pulmonary sepsis	10051739
respiratory syncytial virus bronchiolitis	10038718
respiratory syncytial virus bronchitis	10069811
respiratory tract infection	10062352
respiratory tract infection viral	10062106

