1. INTRODUCTION

1.1. Background

1.1.1. RSV disease burden

Respiratory syncytial virus (RSV) is a ribonucleic acid virus of which two antigenically distinct subgroups exist, referred to as RSV-A and RSV-B [Borchers, 2013]. RSV is a highly contagious human pathogen that causes respiratory tract infections (RTI) in people of all ages.

During the first year of life, 50-70% of infants are infected with RSV and essentially all children have had an RSV infection by their second birthday. The risk for severe RSV-associated lower respiratory tract infections (LRTI) is highest in infants below 6 months of age and is a leading cause for hospitalization. It is estimated that on average 31 per 1000 children below 6 months of age are hospitalized for RSV-associated severe LRTI [Boyce, 2000; Deshpande, 2003; Hall, 2009; Holman, 2004; Iwane, 2004; Paramore, 2004; Vicente, 2003]. 50-70% of these hospitalized children do not have additional risk factors like preterm birth or cardiopulmonary disease [Boyce, 2000; García, 2010; Hall, 2009; Rietveld, 2004]. For human immunodeficiency virus (HIV)-infected children, the incidence rate of hospitalization for RSV-associated LRTI was reported to be 2.5- to 5-fold greater than in HIV-uninfected children [Cohen, 2015; Madhi, 2006]. Although RSV hospitalization rates substantially decrease after 6 months of age, a considerable number of RSV infections in children of 6-15 months of age, still lead to bronchiolitis or (broncho)pneumonia requiring medical attention [Fisher, 1997].

Previous infection with RSV does not prevent subsequent infections. Therefore, re-infection with RSV occurs throughout an individual's lifetime and is common in all age groups [Simoes, 1999; Krilov, 2011]. These re-infections generally go undiagnosed because they usually present as common acute upper respiratory tract infections. In more vulnerable persons (e.g. immunocompromized subjects or elderly), re-infections can however also lead to severe disease [Graham, 2011].

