Figure 2 Schematic overview of required additional hematology and biochemistry testing during the study

Note: For safety reasons and specifically for further investigation of an AE of specific interest (suspected bleeding or low platelet count), blood can be re-sampled for hematology and biochemistry assessment.

6.6.11.3. Nasal swab and other specimen for local assay**Nasal swab and other specimen for local assay collected during assessment visit**

If during passive or active surveillance contact, the investigator/study staff assesses that an infant presents a potential RSV-RTI (refer to 9.2), a nasal swab and another specimen for local assay will be collected during an assessment visit:

- The nasal swab will allow assessing the potential RSV infection by quantitative RT-PCR at sponsor laboratory.
- The specimen for local assay will allow assessing the potential RSV infection and RVP at a local routine laboratory, where available. The specimen type will depend on the assay run locally.

Nasal swab collected to detect asymptomatic RSV infections

During RSV season, there will be monthly nasal swabs to detect asymptomatic RSV infections. These nasal swabs will allow assessing the potential RSV infection by quantitative RT-PCR at sponsor laboratory.

Refer to the SPM for more details about nasal swab.

6.6.12. Detection of spontaneous bleeding or easy bruising and evidence of bruising or petechiae

Subjects' parent(s)/LAR(s) will be instructed to contact the investigator/study staff if their child presents symptoms of spontaneous bleeding or easy bruising or if their child develops a rash in the month following vaccination, in order to detect any thrombocytopenic petechiae or purpura. Refer to Sections 9.1.5 and 9.4.3 for reporting of adverse events of specific interest (spontaneous or excessive bleeding).

At Visit 2 (Day 1), Visit 3 (Day 3)*, Visit 4 (Day 7), Visit 6 (Day 31), Visit 7 (Day 33)*, and Visit 8 (Day 37), the investigator will perform a clinical examination with special attention given to detection of spontaneous bleeding or easy bruising and evidence of bruising or petechiae. Episodes of spontaneous bleeding or easy bruising and evidence of bruising or petechiae will be recorded in the eCRF.

* The visits on Day 3 and Day 33 may be replaced by a phone call by the investigator/study staff to inquire of the infants' general health and to solicit reports of a rash, spontaneous bleeding or easy bruising.

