The percentage of subjects with unsolicited AEs within 30 days (Day 1-30) after each vaccine dose (overall doses) with its exact 95% CI will be tabulated by group and by MedDRA preferred term. Similar tabulation will be done for Grade 3 unsolicited AEs, for any causally related unsolicited AEs, for Grade 3 causally related unsolicited AEs and for unsolicited AEs resulting in a medically attended visit. The verbatim reports of unsolicited AEs will be reviewed by a physician and the signs and AEs will be coded according to the MedDRA Dictionary Version 20 for Adverse Reaction Terminology. Every verbatim term will be matched with the appropriate Preferred Term.

The percentage of subject with episode of spontaneous or excessive bleeding (AE of specific interest), during a 30-day follow-up period after each vaccination will be tabulated by group according to associated PT code presented in Section 12. The percentage of subjects with RSV-LRTI (AE of specific interest) from Dose 1 up to Day 365 and from Dose 1 up to study conclusion (Day 730) will be tabulated by group according to associated PT code presented in Section 12.

The percentage of subjects with SAE within 30 days (Day 1-30) after each vaccine dose with its exact 95% CI will be tabulated by group and by MedDRA preferred term. Similar table will be generated for SAE from Dose 1 up to Day 61, from Dose 1 up to Day 366 and from Dose 1 up to Day 731.

SAEs reported throughout the study and AE of specific interest will be described in detail.

The percentage of subjects using concomitant medication (any medication, any antipyretic/ analgesic and any antipyretic taken prophylactically, respectively) during the 7-day follow-up period (Day 1-7) and during the 30-day follow-up period (Day 1-30) will be summarized by group after each vaccine dose and overall.

For each group and for each hematology and biochemistry parameter:

- The percentage of subjects having hematology and biochemistry results below/above/within the local laboratory normal ranges will be tabulated by timepoint and toxicity grading scale.
- The maximum grading from Screening up to Visit 9 (Day 61) will be tabulated by grading the safety laboratory values according to toxicity criteria Grading scale adapted from [Division of AIDS, 2003], [Division of AIDS, 2004] and [Division of AIDS, 2007].

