## 12. ANNEX 2: RELEVANT PREFERRED TERMS FOR DETECTION OF AESI

Any of the below listed preferred term reported as an Expedited Adverse Event must be immediately escalated to the CRDL or Central Safety Physician to assess or confirm the need for an urgent IDMC review.

The list of preferred terms and associated PT codes is given below:

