**CONFIDENTIAL**

204838 (RSV PED-002)  
Statistical Analysis Plan Final

**Template 33 Listing of AEs related to LRTI and association to RSV infection from vaccination dose 1 up to Day X visit/study end <Exposed Set>**

Group	Sub. No.	Age at onset (month)	Verbatim	Preferred term	MED type	Previous Dose	Day of onset	Start date	End date	Duration	Intensity	Causality	Outcome	Local RSV test result	Date of sample for local testing	Central test RSV A	Central test RSV B	Date of sample for central testing	AESI

RSV-Ld = Low dose ChAd155-RSV vaccine (5 x 10^9 vp)

RSV-Md = Middle dose ChAd155-RSV vaccine (1.5 x 10^10 vp)

RSV-Hd = High dose ChAd155-RSV vaccine (5 x 10^10 vp)

Placebo-Ld = Non-active control (0.5 ml)

Placebo-Md = Non-active control (0.15 ml)

Placebo-Hd = Non-active control (0.5 ml)

AESI: AEs of Special Interest - LRTI identified by the Investigator

\*AEs related to LRTI will be identified based on the list of preferred terms described in in section 12 –Annex 2

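### SAP Annex 2 omits several lower-respiratory and bleeding terms, so the AESI tables and Templates 33 and 35 can under-count, and a narrow class of SAE misses the term-based escalation step

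*SAP*

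**What the plan says.** Annex 2 gives four term lists: haematoma, haemorrhage, thrombocytopenia and lower respiratory tract infection (LRTI). The SAP uses them in three ways.

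- **Escalation.** An expedited event with a listed term "must be immediately escalated to the CRDL or Central Safety Physician to assess or confirm the need for an urgent IDMC review".
- **AESI percentages.** In SAP 6.4.1.1, the share of subjects with a bleeding AESI, and likewise with an RSV-LRTI AESI, "will be tabulated by group according to associated PT code presented in Section 12". Bleeding is a component of the primary endpoint (SAP 4.1) and RSV-LRTI is a secondary endpoint (SAP 4.2).
- **Listings.** The footnote to Template 33 says "AEs related to LRTI will be identified based on the list of preferred terms". Template 35 does the same for bleeding, and Template 32 uses the lists for its potential-AESI column.

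The only bronchiolitis entry is "respiratory syncytial virus bronchiolitis", and the only purpura entry is "thrombocytopenic purpura".

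The protocol does not define an AESI by coded term. Section 9.1.5.1 makes any spontaneous or excessive bleeding within 30 days of a dose an AESI. Section 9.1.5.2 bases RSV-LRTI on the investigator's judgment and a local RSV test.

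**The concern.** Templates 33 and 35 carry a separate column for the investigator's AESI flag, so the term lists are evidently meant to find events beyond those flagged. A list with ordinary terms missing cannot do that.

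The omissions do not look like a deliberate narrow choice. The LRTI list admits unspecified respiratory tract infection, and the bleeding lists include ovarian and prostatic haemorrhage. Yet they have no plain bronchiolitis and no nosebleed.

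Protocol 1.1.1 says that RSV infections at 6 to 15 months "still lead to bronchiolitis or (broncho)pneumonia requiring medical attention", an age range that overlaps the trial's 12 to 23 months. Protocol 6.6.12 makes bruising a scheduled examination target, and asks parents to report a rash "in order to detect any thrombocytopenic petechiae or purpura".

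At stake are under-counts in a primary-endpoint component and a secondary endpoint, incomplete listings for comparison with local and central RSV results, and a hole in one of the routes to urgent IDMC review.

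**Working it through.** No sample-size or power figure is involved. The check is a count and string search of the lists, followed by a trace of the routes by which an event can reach the IDMC.

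**1. List contents.** Haematoma 74 terms, haemorrhage 131, thrombocytopenia 9, LRTI 14. Total: 74 + 131 + 9 + 14 = 228.

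| Search string | Hits | Terms found |
|---|---|---|
| bronchiol | 1 | RSV bronchiolitis |
| purpur | 1 | thrombocytopenic purpura |
| petech | 1 | petechiae |
| epistax, nose | 0 | none |
| nasal | 2 | nasal septum and paranasal sinus haematoma |
| bruis, contus, ecchym | 0 | none |

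Read in full, the 14 LRTI terms hold pneumonia as unspecified, atypical, haemorrhagic and RSV, with no bronchopneumonia and no viral pneumonia. Bleeding in the mouth is covered by lip, mouth and tongue terms, with none for the gums.

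**2. Effect on outputs.** The tables in SAP 6.4.1.1 and Templates 33 and 35 depend on these codes. An event coded outside them is left out as the text stands, even if the investigator flagged it.

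**3. Effect on escalation.** Annex 2 acts only on expedited events, and protocol 9.4.1 (Table 20) provides expedited reports only for SAEs and AESIs. By type of event:

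- *Flagged AESI, any coded term.* Reported within 24 hours, and sent to the iSRC and IDMC within 48 hours of the sponsor's awareness (protocol 9.10.2, 9.10.3). A missing Annex 2 term does not block this.
- *Non-serious and unflagged.* No expedited report exists, so no term list could escalate it. General AE recording covers only 30 days after each dose (protocol 9.3.1).
- *Unflagged SAE that is fatal, life-threatening, related, or within 30 days of a dose.* Itemised in protocol 9.10.3 for 48-hour transmission.
- *Any other unflagged SAE.* Not itemised in 9.10.3. Protocol 1.2.4.2 says more generally that SAEs go within 48 hours, so the two sections do not settle it. Cumulative SAE tables follow about monthly during RSV surveillance.

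Only the last type needs Annex 2. An example is a bronchiolitis admission more than 30 days after a dose, not life-threatening, judged unrelated and with no local RSV result. Protocol 9.2.5 requires local RSV testing of suspected LRTI in hospitalised subjects, but 6.6.11.3 provides local testing only where it exists. What remains is an absent or pending result.

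**4. Scale.** With about 8 to 16 vaccinees per group at Steps 1 and 2 and about 16 at Step 3 (protocol 6.2.2.2.1), one missed subject is 1/16 = 6.25% or 1/8 = 12.5% of a group. Among the 32 to 48 vaccinees in all (protocol 1.3) it is 1/48 = 2.1% to 1/32 = 3.1%.

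**The case against.** A reader might infer that events with missing terms would escape safety review altogether. The documents do not support that: flagged AESIs and most SAEs reach the IDMC whatever their coded term, and holding rule 1d uses no term list.

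Nor does the respiratory analysis rest on Annex 2. Symptomatic cases are swabbed and classified by case definition, Template 34 selects by case definition or AESI flag and shows local and central RSV results, and Template 51 does not use the list. Bruising and petechiae found at visits are recorded in the eCRF, and Appendix Table IIE lists the detected episodes. Unsolicited AEs within 30 days are tabulated by preferred term in any case. All of this stands, and it confines the point to the outputs and the one type of SAE identified above.

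A reader might also infer that the protocol itself names every missing event. It does not. Bronchiolitis appears only in the disease background. Purpura is named together with petechiae as thrombocytopenic, and both of those terms are listed. Nosebleed is not named. Bruising is named, but a bruise coded to a haematoma or skin-haemorrhage term would be caught.

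Finally, a broad extension would do harm. Through SAP 6.4.1.1, contusion or injection-site bruising would count ordinary toddler bruises as bleeding AESIs, and a general RSV-infection term would count infections outside the lower tract as RSV-LRTI. This also stands, and it limits the fix.

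**Conclusion.** The omissions are real and can be read off Annex 2. Followed as written, the SAP can under-count the bleeding AESI and the RSV-LRTI AESI and leave events out of Templates 33 and 35. This matters more than the lost escalation, which is limited mainly to an SAE not flagged as an AESI and outside the itemised 48-hour list.

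The number of events affected cannot be estimated from the documents, but in groups this small a single one is visible in the percentages. The conclusion rests on two assumptions:

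- SAP 6.4.1.1 is read as selecting events by the Annex 2 codes.
- At least some such events would be coded to terms that are not listed. That depends on MedDRA, which the documents do not reproduce.

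**What to change.** 1. Add unspecified and viral bronchiolitis, bronchopneumonia and viral pneumonia to the LRTI list, and nosebleed, gum bleeding and purpura to the bleeding lists. First check the exact terms against MedDRA Version 20, the version named in SAP 6.4.1.1.
2. Select Templates 33 and 35 and the AESI tables of SAP 6.4.1.1 on the investigator's AESI flag as well as on the term list.
3. Hold bruise or contusion, increased tendency to bruise, injection-site bruising and general RSV-infection terms in a separate list for escalation and listing review only. Do not count them in the AESI percentages unless the investigator flagged the event.

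The cost is an edit to the annex and to the selection rules. A few more events will need triage and listing, and AESI counts will rise slightly. Unspecified bronchiolitis would enter the RSV-LRTI table without proof of RSV, as unspecified bronchitis and pneumonia already do.

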## 13. ANNEX 3: STUDY SPECIFIC MOCK TFL

The data display, title and footnote is for illustration purpose and will be adapted to the study specificity as indicated in the TFL TOC. Note that there may be few changes between the study specific SAP mock TFL and the final TFLs as editorial/minor changes do not require a SAP amendment.

### 13.1. List of individual data listing

Following individual data listing will be generated

Appendix Table I.A - Elimination codes  
Appendix Table I.B – Demography  
Appendix Table IBii - Physical examination/vital signs  
Appendix Table I.Ci - Dates of birth, Informed consent, Vaccination and blood sampling, Contact  
Appendix Table I.Cii - Reason for visit not done  
Appendix Table I.D - General medical history - Physical examination  
Appendix Table I.Ei – Study Conclusion  
Appendix Table I.Eii – Screening conclusion  
Appendix Table I.F – Notes (this appendix is provided for info only and should not be used for the clinical report)  
Appendix Table I.G / I.H - Vaccination procedure  
Appendix Table I.I - Reason for not administration of vaccine  
Appendix Table I.J - Reason for non-eligibility  
Appendix Table I.Ki – Previous history of vaccination  
Appendix Table I.Kii – Previous history of disease  
Appendix Table II.Ai - Solicited local adverse events  
Appendix Table II.B - Solicited general adverse events  
Appendix Table II.Ci - Unsolicited adverse events within (30) days post-vaccination  
Appendix Table II.Cii - Unsolicited adverse events after (30) days post-vaccination  
Appendix Table II.Di - Concomitant medications  
Appendix Table II.Dii - Concomitant vaccinations  
Appendix Table III.A – Immunogenicity - HI  
Appendix Table III.B – Immunogenicity- CMI  
Appendix Table IV.A – Haematology and Biochemistry  
Appendix Table IIIA – Altitude of the site  
Appendix Table IIE –Detection of Episodes and Limb Examination  
Appendix Table IIF - Surveillance Contact  
Appendix Table IIG - Assessment of RTI Episode  
Appendix Table IIH - RTI Symptoms  
Appendix Table IIJ - Signs and Symptoms of RSV-LRTI  
Appendix Table IIK - Chest X-Ray Observations  
Appendix Table IIL- Inpatient Care  
Appendix Table IIIA – Local RSV Result  
Appendix Table IIIB – Nasal Swab (qRT-PCR Result)  
Appendix IIIC – Blood culture result  
Appendix IIID- Re-screening

### 13.2. Template of Tables and Figures

**Template 1 Number of subjects by country and center <Exposed Set>**

		<Each group> N=XXXX		<Each group> N=XXXX		Total N=XXXX	
Country	Center	n	%	n	%	n	%
<each country>	<each center >	XXX	XX.X	XXX	XX.X	XXX	XX.X
	All	XXX	XX.X	XXX	XX.X	XXX	XX.X

**<each group>:**

- RSV-Ld = Low dose ChAd155-RSV vaccine (5 x 10^9 vp)
- RSV-Md = Middle dose ChAd155-RSV vaccine (1.5 x 10^10 vp)
- RSV-Hd = High dose ChAd155-RSV vaccine (5 x 10^10 vp)
- Placebo-Ld = Non-active control (0.5 ml)
- Placebo-Md = Non-active control (0.15 ml)
- Placebo-Hd = Non-active control (0.5 ml)
- n = number of subjects in a given center or country
- N = total number of subjects
- % = n/N x 100
- Center = GSK Biologicals assigned center number

**Template 2 Number of subjects vaccinated, completed and withdrawn with reason for withdrawal – up to Day X <Exposed set>**

	<Each group> N=XXXX	<Each group> N=XXXX	Total N=XXXX
	n	n	n
Number of subjects vaccinated	xxx	xxx	xxx
End of study status			
[EACH CATEGORY]	xxx	xxx	xxx
Reasons for withdrawal:			
[REASONS]	xxx	xxx	xxx

**<each group>:**

- RSV-Ld = Low dose ChAd155-RSV vaccine (5 x 10^9 vp)
- RSV-Md = Middle dose ChAd155-RSV vaccine (1.5 x 10^10 vp)
- RSV-Hd = High dose ChAd155-RSV vaccine (5 x 10^10 vp)
- Placebo-Ld = Non-active control (0.5 ml)
- Placebo-Md = Non-active control (0.15 ml)
- Placebo-Hd = Non-active control (0.5 ml)
- Vaccinated = number of subjects who were vaccinated in the study
- Completed = number of subjects who completed last study visit
- Withdrawn = number of subjects who did not come for the last study visit

**Template 3 Visit attendance <Exposed set>**

		<Each group> N=XXX	
Visit	Status	n	%
INFORMED CONSENT	Completed		
RANDOMIZATION	Completed		
<EACH VISIT>	Attended		
	Not attended yet		
	Permanent discontinuation prior to this visit		
	Not attended		
CONCLUSION	Completed		

**<each group>:**

RSV-Ld = Low dose ChAd155-RSV vaccine (5 x 10^9 vp)  
 RSV-Md = Middle dose ChAd155-RSV vaccine (1.5 x 10^10 vp)  
 RSV-Hd = High dose ChAd155-RSV vaccine (5 x 10^10 vp)  
 Placebo-Ld = Non-active control (0.5 ml)  
 Placebo-Md = Non-active control (0.15 ml)  
 Placebo-Hd = Non-active control (0.5 ml)  
 N = Number of subjects in each group or in total  
 Conclusion = date of last visit or withdrawal

**Template 4 Number of subjects enrolled into the study as well as the number of subjects excluded from the PPS analysis of immunogenicity at Day X with reasons for exclusion**

Title	Total			<each group>	
	n	s	%	n	s
Enrolled Set					
Invalid informed consent or fraudulent data (code 900)					
Study vaccine dose not administered but subject number allocated (code 1030)					
Exposed set					
<Reason for elimination & elimination code>					
<Reason for elimination & elimination code>					
PPS for analysis of immunogenicity at Day X					

**<each group>:**

RSV-Ld = Low dose ChAd155-RSV vaccine (5 x 10^9 vp)  
 RSV-Md = Middle dose ChAd155-RSV vaccine (1.5 x 10^10 vp)  
 RSV-Hd = High dose ChAd155-RSV vaccine (5 x 10^10 vp)  
 Placebo-Ld = Non-active control (0.5 ml)  
 Placebo-Md = Non-active control (0.15 ml)  
 Placebo-Hd = Non-active control (0.5 ml)  
 Note: Subjects may have more than one elimination code assigned  
 n = number of subjects with the elimination code assigned excluding subjects who have been assigned a lower elimination code number  
 s = number of subjects with the elimination code assigned  
 % = percentage of subjects in the considered PPS relative to the Exposed set

**Template 5 Summary of demographic characteristics <Exposed set>**

	<Each group> N=XXXX		<Each group> N=XXXX		Total N=XXXX	
	Value or n	%	Value or n	%	Value or n	%
Age in months at <timepoint>						
N with data	xxx		xxx		xxx	
Mean	xxx.x		xxx.x		xxx.x	
SD	xxx.x		xxx.x		xxx.x	
Median	xxx.x		xxx.x		xxx.x	
Minimum	xxx		xxx		xxx	
Maximum	xxx		xxx		xxx	
Gender						
<EACH GENDER>	xxx	xx.x	xxx	xx.x	xxx	xx.x
...	xxx	xx.x	xxx	xx.x	xxx	xx.x
Ethnicity						
<EACH ETHNICITY>	xxx	xx.x	xxx	xx.x	xxx	xx.x
...	xxx	xx.x	xxx	xx.x	xxx	xx.x
Geographic Ancestry						
<EACH GEOGRAPHIC ANCESTRY>	xxx	xx.x	xxx	xx.x	xxx	xx.x
...	xxx	xx.x	xxx	xx.x	xxx	xx.x
Country						
<EACH COUNTRY>	xxx	xx.x	xxx	xx.x	xxx	xx.x
...	xxx	xx.x	xxx	xx.x	xxx	xx.x

